1. BACKGROUND AND RATIONALE

Conventional nipple and/or skin-sparing mastectomy (NSM/SSM) with or without immediate reconstruction is becoming one of the mainstream surgical treatment for breast cancer and risk reducing mastectomy in recent years. While this technique provides satisfactory oncologic and aesthetic outcomes, its disadvantages include skin flap and/or nipple-areolar complex (NAC) necrosis, NAC malposition/distortion as well as visible scar(s) on the breast.

In terms of technical aspects, NSM/SSM has its inherent challenges in view of limited incisions and thereby difficulties in dissection. Since 2015, a number of institutions worldwide had adopted a new technique of NSM/SSM using robotic surgical system. Institutional experiences worldwide demonstrated feasibility and safety of this technique coupled with improved patients' satisfactions.

To date, there is no center in Singapore or the region offering Robotic NSM/SSM (R-NSM/R-SSM). The authors believe that robotic mastectomy is a feasible and safe technique that can be utilized in our institution and it provides superior aesthetic outcomes with less morbidity and higher patient satisfaction if compared to conventional NSM/SSM.

The aim of this study is to conduct a single-arm prospective pilot study to investigate the safety and feasibility, as well as aesthetic outcomes, surgical complications and patients' satisfactions of R-NSM/R-SSM.

2. HYPOTHESIS AND OBJECTIVES

Hypothesis

Based on institutional cohort studies to date, we believe that robotic mastectomy is a safe surgical alternative to conventional surgery in terms of surgical outcomes while offering comparable if not superior aesthetic outcomes and improved patients' satisfactions.

Objectives

The proposed study aims to report to ascertain on the surgical outcomes, aesthetic and health related quality of life outcomes as well as satisfaction in patients undergoing robotic mastectomy.

Primary Outcomes:

1. Surgical Outcomes

- Operative parameters - docking time, console time, reconstruction time, total operative time
- Length of stay – defined as the length of hospitalization from admission till discharge
- 30-days morbidity/complications

Secondary Outcomes:

1. Oncologic outcomes
 - Positivity of margins as a surrogate for short term oncologic safety
2. Health-Related Quality of Life (QOL) and Patient Satisfaction using validated Breast-Q questionnaire at 1 and 6 months after operation

Surgical Outcomes

- Operative parameters
 - Docking time – defined as time taken to dock the robot before robotic mastectomy
 - Console time – defined as time taken for robotic mastectomy robot docking time, conversion)
 - Reconstruction time – defined as time taken for breast reconstruction, if applicable
 - Total operative time – defined as time taken from axilla staging procedure, robot docking time, console time, closure and time taken for reconstruction, if applicable.
 - Length of stay – defined as the length of hospitalization from admission till discharge
- 30-days morbidity/complication
 - Wound infection requiring intervention – defined as wound infection where conservative treatment fails and requires surgical debridement
 - Flap and nipple areolar complex (NAC) necrosis – defined as ischaemia of mastectomy skin flap or nipple areolar complex necrosis
 - Postoperative hematoma/bleeding requiring intervention – defined as immediate post-operative bleeding or haematoma requiring emergent exploration and haemostasis
 - Anesthesia related complications – defined as complications related to anaesthesia conduct

Oncologic outcomes

- Positivity of margins – defined as margins involved or uninvolved. Margins involvement is defined as tumor-on-ink for invasive carcinoma and 2 mm margin or less for ductal carcinoma-in-situ

Health-Related Quality of Life (QOL) and Patient Satisfaction using validated Breast-Q questionnaire at 1 and 6 months after operation

- Health-Related QOL- defined as QOL from psychosocial, physical and sexual well-being perspectives
- Patient satisfaction – defined as satisfaction with breasts, satisfaction with outcome and satisfaction with care

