3. EXPECTED RISKS AND BENEFITS

Risks associated with robotic mastectomy are similar to conventional surgical options which are as below:

- Post-surgical Pain
- Post-surgical Bleeding / Haematoma
- Wound Infection / Abscess
- Wound Breakdown and /or Necrosis
- Scar and Keloid formation.
- Shoulder Stiffness
- Numbness
- Seroma

Benefits include, but not limited to:

- Smaller incision which may translate to lesser pain and faster recovery
- Improved patients' satisfaction

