Adverse Event Assessment		X	X	X
Clinical Assessment	X		X	
Collection of medical information	X	X	X	X

As part of standard care, patients will be followed up as per conventional surgery. This includes twice weekly review of wound by the breast surgeon/ breast care nurses, with the earliest visit scheduled on post-operative day 4 and to continue until wound(s) have completely healed.

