6. SAFETY MEASUREMENTS

6.1. Definitions

Serious adverse event (SAE) in relation to human biomedical research, means any untoward medical occurrence as a result of any human biomedical research which:

- results in or contributes to death
- is life-threatening
- requires in-patient hospitalisation or prolongation of existing hospitalisation
- results in or contributes to persistent or significant disability/incapacity or
- results in or contributes to a congenital anomaly/birth defect
- results in such other events as may be prescribed

Adverse event (AE) in relation to human biomedical research means any untoward medical occurrence as a result of any human biomedical research which is NOT serious. Adverse event can be any unfavourable and unintended sign (including an abnormal laboratory finding), symptom, or disease possibly/ probably/ definitely associated with the participant in the human biomedical research.

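### The primary 30-day morbidity list is narrower than the protocol's own list of expected risks, and no text carries the other complication records into that outcome or its analysis

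*Combined protocol and SAP*

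**What the plan says.** Section 2 lists "30-days morbidity/complications" among the primary outcomes and then gives four components:

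- wound infection, meaning "wound infection where conservative treatment fails and requires surgical debridement";
- flap and nipple-areolar complex (NAC) necrosis, "defined as ischaemia of mastectomy skin flap or nipple areolar complex necrosis";
- bleeding or haematoma, meaning "immediate post-operative bleeding or haematoma requiring emergent exploration and haemostasis";
- anaesthetic events, "defined as complications related to anaesthesia conduct".

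There is no residual category, and nothing marks the list as open-ended.

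Section 3 names eight expected risks. They include seroma, infection or abscess with no treatment threshold, and "Wound Breakdown and /or Necrosis". It describes the risks as like those of conventional surgery.

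Three other places bear on capture:

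- Section 5 includes complications among the data collected, without defining the term or requiring relatedness. It also schedules adverse-event assessment at Visits 2 to 4 and, as standard care, "twice weekly review of wound by the breast surgeon/ breast care nurses".
- Section 6.1 defines an adverse event as "any untoward medical occurrence as a result of any human biomedical research which is NOT serious". Its next sentence accepts events that are only possibly associated.
- Section 6.2 has non-serious related events kept in the site file.

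Section 8.2 plans descriptive statistics, with 95% confidence intervals for the primary and secondary endpoints. It does not mention adverse events.

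**The concern.** Safety is a headline aim of this single-arm pilot, and Section 1 states a prior belief that the robotic technique carries less morbidity. If the primary list is applied as written, a case with a seroma, a non-ischaemic wound breakdown, an infection settled without debridement or a late haematoma contributes nothing to the primary 30-day outcome. A reader of the results would probably take 30-day morbidity to mean all complications to day 30, and could set it against series that count more broadly.

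The adverse-event record is the natural backstop, but entry to it turns on whether the event is judged to result from the research. Because Section 3 likens the risks to those of conventional surgery, an investigator could in good faith attribute a seroma to mastectomy in general. A single-arm study has no control group against which to check that judgement.

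**Working it through.** **1. Risks in Section 3 against components in Section 2**

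| Expected risk (Section 3) | Counted in the 30-day list (Section 2)? |
|---|---|
| Pain | No component |
| Bleeding/haematoma | In part: only if immediate and emergently explored |
| Infection/abscess | In part: only if conservative treatment fails and debridement is needed |
| Wound breakdown/necrosis | In part: ischaemia or necrosis only |
| Scar/keloid | No component |
| Shoulder stiffness | No component |
| Numbness | No component |
| Seroma | No component |

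Five of the eight have no component and three are covered in part.

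**2. The other records**

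| Source | Can it hold an unlisted event? | Is it linked to the 30-day outcome or Section 8.2? |
|---|---|---|
| Complications in the study data (Section 5) | Yes, with no relatedness condition, but the term is undefined | No |
| Adverse-event assessment (Sections 5, 6.1, 6.2) | Yes, if judged at least possibly associated | No |
| Wound reviews (Section 5) | Yes, as standard care | No |

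**3. The plan's own figure**

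Inputs from Section 8.1: n = 20 cases, p = 0.20, 80% confidence, continuity correction. The normal-approximation interval is p ± [z × √(p(1−p)/n) + 1/(2n)], with z = 1.2816.

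- √(0.20 × 0.80/20) = 0.0894
- 1.2816 × 0.0894 = 0.1146
- 1/(2 × 20) = 0.0250
- half-width = 0.1396

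The interval is 6.0% to 34.0%, width 27.9%. This reproduces the stated 6% to 34% and 28%. The arithmetic is sound; what is missing is which events make up the 20%.

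**4. Size of the gap**

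One case is 1/20 = 5 percentage points. Only cases whose sole complications are unlisted move an any-complication proportion; a case that also has a listed event is already counted.

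The documents give no rate for the unlisted events, so the counts below are assumptions. They start from 4 listed cases (the 20% of Section 8.1). Intervals are exact (Clopper-Pearson) at the 95% level of Section 8.2, which does not name a method.

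| Cases with unlisted events only | Any complication | 95% exact interval |
|---|---|---|
| 0 | 4/20 = 20% | 5.7% to 43.7% |
| 1 | 5/20 = 25% | 8.7% to 49.1% |
| 2 | 6/20 = 30% | 11.9% to 54.3% |
| 3 | 7/20 = 35% | 15.4% to 59.2% |

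The same can be put as rates. If listed events occur in 20% of cases and unlisted ones independently in a proportion e, the any-complication rate is 1 − 0.80 × (1 − e). This gives 24% at e = 5%, 36% at e = 20% and 52% at e = 40%. The spread shows how far the answer depends on a rate the documents do not supply.

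**The case against.** The strongest reply is that this is a defensible design choice. A 20-case pilot may reasonably set an intervention threshold for infection and bleeding and describe other complications separately. A narrower, openly defined endpoint is a different quantity and not a biased estimate of a broader one. There is no test or benchmark, and no text says that the four components are combined into a single rate. Section 10 also mentions a data dictionary, not shown here, that may define complications more fully.

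Much of this stands. In particular, three stronger readings should not be drawn:

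- A reader might infer that the omitted events are recorded nowhere and cannot be recovered. The documents do not support that. Section 5 collects complications without a relatedness condition and schedules adverse-event assessment at Visits 2 to 4. Section 6.1 admits possibly associated events, and robotic mastectomy is itself the research procedure, so a seroma after it can qualify.
- A reader might infer that the plan directs investigators to exclude such events. It does not; it leaves room for that judgement.
- A reader might infer that the four components are the major complications. They are not defined that way: flap or NAC necrosis and anaesthetic events carry no severity threshold.

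The boundary is also uncertain in places. The infection component's label speaks of intervention and its definition of debridement, so the status of a drained abscess is unclear.

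The reply does not supply the missing link. The only definition of 30-day complications in the documents is the four-item list, and nothing brings the other records into the primary outcome or the analysis.

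**Conclusion.** The point holds as one about endpoint definition and reporting. The primary 30-day outcome leaves out complications that the protocol itself expects. The records that may hold them depend on a relatedness judgement (adverse events) or on an undefined term (complications), and neither is tied to the 30-day outcome or to Section 8.2.

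The reported 30-day morbidity can therefore understate all 30-day complications, by 5 percentage points for each case with unlisted events only. This assumes 20 analysed cases and an any-event proportion. If results are given by component instead, the omitted types simply have no row. The number of such cases is unknown, and 20% against 35% is an illustration, not an estimate. The Section 8.1 interval is correctly computed, but its 20% has no stated event definition. The change should be made before results are reported.

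**What to change.** 1. **Section 2.** Keep the four components as a named, prespecified subset, without calling them major. Add to the primary 30-day outcome *any postoperative complication within 30 days, regardless of attribution*. It should cover at least seroma, wound breakdown, infection not debrided, and haematoma or bleeding not emergently explored. Report each by type and by the management it received. State whether a drained abscess falls under the existing infection component or the new category.
2. **Section 5.** Define complications in the data set in the same terms, and name the wound reviews and Visit 3 as sources for the 30-day outcome.
3. **Section 6.** State that all untoward events to day 30 are recorded first and relatedness is assessed afterwards. Leave the reporting rules to the ethics board (CIRB) unchanged.
4. **Section 8.1.** Say whether the 20% refers to the four-component subset or to any complication.
5. **Section 8.2.** Report both proportions with 95% confidence intervals.

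The cost is protocol and case report form wording and one more table row, using reviews and visits already scheduled. The reported rate is likely to be somewhat less favourable. Sample size and clinical care are unaffected.

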
Reconstruction

In this study, suitable participants can opt for immediate reconstruction with implant or autologous tissue (latissimus dorsi flap) reconstruction

- Immediate Implant Reconstruction

Following removal of the specimen and adequate haemostasis, copious irrigation of the mastectomy pocket will be performed. Subsequently, the lateral border of the pectoralis major muscle is elevated to allow for submuscular pocket dissection. The working space is then developed under direct vision by electrocautery with assistance of a handle light retractor. The single port will then be re-inserted with CO2 insufflation for robotic sub-muscular pocket dissection using the da Vinci surgical platform. Dissection is performed medially towards the sternal border, taking care not to injure the perforator vessels. Inferiorly, the dissection is carried out beyond the inframammary fold over the lateral aspect, below which the muscle will be released to continue the dissection to the subcutaneous plane thus allowing for a more natural placement of the implant. In the lateral border, the superficial fascia of the serratus anterior muscle will be dissected posteriorly in a limited fashion so that it will just be enough to accommodate the lateral border of the implant. After initial dissection of the sub-muscular space with the da Vinci surgical platform, the robotic instruments and single port will then be removed. The operating table will be repositioned into the sitting position. The adequacy of the sub-muscular pocket dissection is checked and completed with the assistance of a light source retractor. After creation of the submuscular pocket, an implant (Mentor Worldwide LLC, Santa Barbara, CA) will then be placed followed by drains placement in both submuscular and subcutaneous planes. An acellular dermal matrix (ADM) or mesh might be used based on surgeon's discretion.

- Immediate Pedicled Latissimus Dorsi (LD) Flap Reconstruction

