Following removal of the specimen and adequate haemostasis, copious irrigation of the mastectomy pocket is performed. Subsequently, the thoracodorsal pedicle is identified and marked with a vessel loop to prevent injury during the flap harvest. Patient is then shifted to the lateral decubitus position. Two 12 mm balloon trocars (Kii Balloon blunt tip system, Applied Medical, Rancho Santa Margarita, CA, USA) will be used as working ports. The ports are then docked to the robotic arms, and CO2 insufflation is applied at 10–12 mmHg. Dissection will then start along the under surface of the latissimus dorsi muscle. Blood vessels encountered are carefully dissected, coagulated and cut with monopolar scissors. As the dissection through the under surface of the muscle to the borders is completed, further dissection over the superficial surface of the muscle ensued. The muscle is then disconnected from the infero-posterior and scapular border. Afterwards, the pedicled LD flap is exteriorized from the axilla wound and the robotic arms are then undocked. Reconstruction of the mastectomy defect will be performed with the patient turned back to a supine position. Fixation of the flap to all quadrants is performed with assistance from a handle light retractor to ensure full coverage of the defect. Care must be taken to ensure the correct axis of the vascular pedicle in order to prevent torsion of the blood supply. Drains will then placed both in the donor site as well as mastectomy cavity.

Perioperative monitoring and discharge criteria

Patients will be monitored in 23-hour ward as per current department protocol as conventional mastectomy and discharged on post-operative day 1 if discharge criteria fulfilled.

Discharge criteria include ALL of the following:

Patient MUST have ALL of the following:

- Stable vital signs
- Able to maintain pre-procedure mobility with minimal assistance as appropriate for the procedure
- Able to retain feeds
- Able to pass urine
- Has a responsible adult to accompany him/her home

Patient must NOT have ANY of the following:

- Excessive pain not relieved by oral analgesics
- Excessive nausea/ vomiting
- Severe giddiness
- Respiratory depression/ difficulty
- Bleeding from surgical wound

**Patient who doesn't fulfil ALL of the above will be admitted for further observation*

	Visit 1 (Screening)	Visit 2 (Day of Surgery)	Visit 3 (+/- 2 weeks) (30 th POD)	Visit 4 (+/- 2 Weeks) (6 months POD)
Consent taking	X			
Eligibility Check	X			

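### None of the four defined 30-day morbidity items captures LD flap loss or implant loss as such, so a failed robotic reconstruction can score zero on the primary safety outcome

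*Combined protocol and SAP*

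**What the plan says.** Section 2 lists "30-days morbidity/complications" among the primary surgical outcomes and then defines four components:

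- Wound infection requiring intervention: "defined as wound infection where conservative treatment fails and requires surgical debridement".
- Flap and nipple-areolar complex (NAC) necrosis: "defined as ischaemia of mastectomy skin flap or nipple areolar complex necrosis".
- Haematoma or bleeding requiring intervention: "defined as immediate post-operative bleeding or haematoma requiring emergent exploration and haemostasis".
- Anaesthesia-related complications: "defined as complications related to anaesthesia conduct".

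There is no line for other complications. Reconstruction time is among the primary operative parameters.

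Section 5 (Reconstruction) says that "suitable participants can opt for immediate reconstruction with implant or autologous tissue (latissimus dorsi flap) reconstruction". The implant route includes robotic dissection of the submuscular pocket. The LD route includes robotic harvest of the muscle and a drained donor site, with the instruction that "Care must be taken to ensure the correct axis of the vascular pedicle in order to prevent torsion of the blood supply".

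Other parts of the plan would record problems more generally. Section 5 collects complications without defining them, and its visit table schedules adverse event assessment on the day of surgery, at 30 days and at 6 months. Section 6.1 defines serious events to include those that lead to or prolong hospital admission. Section 8.2 plans descriptive summaries of outcome variables, with 95% confidence intervals for the primary and secondary endpoints.

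**The concern.** The second robotic stage is part of what the pilot tests, and its duration is counted in a primary outcome, but no morbidity item asks whether the reconstruction survived. The necrosis item is headed with the unqualified word flap, yet its definition narrows this to the mastectomy skin flap and the NAC. Two people abstracting the same LD flap loss could classify it differently. The one who follows the definition would not count it.

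At stake is the safety result that the pilot exists to give. If reconstruction failures fall outside the defined items, the 30-day figure can look as good for reconstructed breasts as for mastectomy alone when it is not. The events would also carry no assured rate or interval, because the planned intervals are tied to the listed endpoints.

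**Working it through.** **1. Events set against the four definitions in Section 2**

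| Event | Scores on a listed item? |
|---|---|
| LD flap loss without debridement, emergent exploration or skin/NAC necrosis | No |
| Implant removal or exchange without any of these three | No |
| Implant removed with debridement after failed treatment of infection | Yes, infection |
| Implant loss accompanied by skin-flap or NAC ischaemia | Yes, necrosis |
| Donor-site infection needing debridement | Yes, infection (no site limit) |
| Immediate donor-site haematoma needing emergent exploration | Yes, bleeding (no site limit) |
| Donor-site seroma, non-infected wound breakdown, or infection short of debridement | No |

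Section 3 lists seroma and wound breakdown as expected risks, so the last row is foreseen by the protocol itself.

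**2. Is the list open?** Where the protocol means a list to be illustrative it says so (benefits in Section 3, selection criteria in 4.3, co-morbid conditions in 4.4 and 5). The morbidity list carries no such wording.

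**3. The plan's own figure.** Section 8.1 gives an 80% interval of 6% to 34% (width 28%) at 20% with n = 20, continuity-corrected. The continuity-corrected Wald formula is p ± [z·√(p(1−p)/n) + 1/(2n)]:

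0.20 ± [1.2816 × √(0.20 × 0.80/20) + 1/40] = 0.20 ± [0.1146 + 0.0250] = 0.20 ± 0.1396

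This gives 6.0% to 34.0%, width 27.9%, so the stated figure reproduces. The concern is about what enters the numerator, not about this calculation.

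**4. Effect of one uncounted failure.** 1/20 = 5 percentage points.

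Illustration with assumed counts: if the listed items give 1/20, the rate is 5% (exact 95% interval 0.1% to 24.9%). If three further breasts lost a reconstruction, it is 4/20 = 20% (5.7% to 43.7%).

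**5. How likely is a missed failure?** The documents give neither input. Assume m reconstructed breasts (5 to 20) and a chance f per breast (2% to 10%) of a failure that meets no listed item. The expected number missed is m × f. The chance of at least one is 1 − (1 − f)^m.

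| m | f | Expected missed | Chance of at least one |
|---|---|---|---|
| 5 | 2% | 0.1 | 1 − 0.98^5 = 10% |
| 10 | 5% | 0.5 | 1 − 0.95^10 = 40% |
| 20 | 10% | 2.0 | 1 − 0.90^20 = 88% |

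These figures treat breasts as independent, although Section 4.1 counts a bilateral patient as two cases.

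**The case against.** The strongest reply is that the documents never define a closed composite. The primary outcome is named in general terms, no passage limits reporting to the four items, and Section 5 collects complications without restriction. On this view the plan only fails to say how unlisted complications enter the endpoint. That is fair as far as it goes: the documents do not show that such events would be left out of the report. But the four items are the only definition of the outcome, and someone following them as written would not count an LD flap loss.

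Stronger readings are tempting, and the documents do not support them:

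- A reader might infer that LD flap loss, implant removal and donor-site problems can enter no listed outcome at all. The infection and bleeding items have no anatomical limit and the necrosis item has no severity threshold, so several such events do count (step 1 of the working). An early failure could also lengthen hospital stay, another primary outcome.
- A reader might infer that failures would go unrecorded and that Breast-Q scores would fall without a recorded surgical cause. Complication collection, wound review twice a week until healing, and adverse event assessment to 6 months make a record likely. What is unsettled is its place in the endpoint.
- A reader might infer that reconstruction failure is the main harm of the robotic second stage. The pedicle sentence is a surgical instruction, not a risk estimate, and reconstruction is optional.
- A reader might infer that there is no denominator. Each operated breast is a case (Section 4.1). What is missing is a denominator of reconstructed breasts.

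The general records do not close the gap. Under Section 6.2, related non-serious events are kept in the site file, and Section 8.2 ties the planned intervals to the primary and secondary endpoints.

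**Conclusion.** The concern holds in limited form. No listed 30-day item captures LD flap loss or implant loss as such, and donor-site events count only as debrided infection or emergently explored haematoma. A failed robotic reconstruction can therefore score zero on the primary safety outcome while still appearing in complication or adverse event records. This is more than missing detail, because the definition as written can give a misleadingly favourable result.

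The firm size is 5 percentage points per uncounted failure at 20 cases. The 10% to 88% range rests wholly on the assumed numbers of reconstructions and failure rates. A scenario in which failures occur and the listed items still show 0/20 is possible but not predicted by anything in the documents. The study is descriptive, with no test or success rule, so the consequence is a safety figure that may understate harm, not a wrong decision at a threshold. The change should be made.

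**What to change.** Add a fifth defined item, reconstruction complication, to the 30-day morbidity list in Section 2. It would cover partial or total LD flap loss, unplanned implant removal or exchange, and LD donor-site complication at a threshold that the investigators set.

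Add to Section 8.2:

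- In any overall morbidity rate, a breast counts once even if it meets several items. Without this rule an implant removed with debridement for infection would be counted twice.
- The new item is reported over reconstructed breasts with an exact 95% interval, with counts shown separately for implant and LD.
- Optionally, a descriptive count is given from the adverse event assessment already scheduled at 6 months.

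Stating only that the four items are not exhaustive would remove the ambiguity but leave reconstruction failure without a definition or a rate.

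The cost is a few case report form fields, largely filled from records already collected, and a morbidity rate that may look less favourable. The interval will be wide: if 10 breasts were reconstructed and 2 failed (assumed), the result would be 20% with an exact 95% interval of 2.5% to 55.6%. That is why only counts are suggested for implant and LD separately. Treatment and sample size do not change.
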